1 SYNOPSIS

Study title

Radiesse® Post Approval Safety Study - Radiological Evaluation of Implantation in the Hands

Study phase

Device Post-Market

Study Product

Radiesse Injectable Implant

Indication

Hand augmentation to correct volume loss in the dorsum of the hand

Primary study objective

The objective of this study is to provide a preliminary assessment of the radiographic appearance of Radiesse material that has been injected into the dorsum of the hands. The assessment will be with standard, plain radiography (X-rays). The hypothesis is that the radiographic appearance of Radiesse in the hands does not obscure the bones of the hands as seen on plain X-rays of the hand.

Primary study endpoint

The primary endpoint is the safety assessment of the incidence of obscuration of the bones of the hand at 1-, 6-, 12-, and 24-months following injection of Radiesse in the dorsum of the hand.

Study population, diagnosis, and main criteria for in- and exclusion

The study will enroll 20 qualifying subjects at least 22 years of age with moderate to very severe volume loss in the dorsum of their hands based on the Merz Hand Grading Scale (MHGS¹, **Figure 1**), 10 with moderate to severe volume loss (MHGS grades 2 and 3) and 10 with very severe volume loss (MHGS grade 4). Key exclusion criteria include hands with previous fat injections, hand deformities, or surgery in the dorsum of the hands, and any medical condition with the potential to interfere with the study or increase the risk of adverse events (AEs). See Section 7 for the full list of inclusion and exclusion criteria.

¹ Carruthers, et al., “A Validated Hand Grading Scale,” Dermatol Surg 2008, 34:S179-S183.

Study design

This is a prospective, descriptive study designed to evaluate whether Radiesse interferes with radiological assessment by obscuring the bones of the hand.

Duration of treatment per subject

Subjects will be in the study for approximately 24 months. Subjects will be treated with Radiesse in the dorsum of the hands after baseline X-rays, and will have the opportunity to receive up to 3 repeat treatments over 2 years of follow-up. The retreatment interval is every six months as agreed upon by the treating investigator and the subject.

Total number of subjects and number of countries

There will be 20 subjects enrolled and treated in the United States.

Number of study sites

This will be a single-site study.

3 ETHICS

3.1 Institutional Review Board

The following documents must be submitted to the responsible Institutional Review Board (IRB)/ethics committee: this protocol, the Informed Consent Form (ICF), relevant supporting information, and all types of subject recruitment or advertisement information. These documents must be approved by the appropriate IRB before the study is initiated. Any amendments to the protocol must also be approved, where necessary, by the IRB prior to implementing changes in the study. Documentation of these approvals must be provided to the Sponsor prior to the initiation of the amendment. The IRB used must comply with current Good Clinical Practice (GCP) and guidelines.

The investigator's responsibilities (at a minimum) regarding the IRB are as follows:

- Obtain IRB approval of the protocol, informed consent, and any advertisements to recruit subjects prior to their use.
- Obtain IRB approval for any protocol amendments and ICF revisions before implementing the changes.
- Provide the IRB with any required information before and during the study.
- Submit progress reports to the IRB, as required, during the conduct of the study; request re-review and approval of the study, as needed; provide copies of all IRB re-approvals and relevant communication to the Sponsor.
- Notify the IRB within 10 days of all serious and unexpected AEs related to the study device that are reported to the investigator by the Sponsor. The investigator is responsible for updating the IRB on the progress of the study and of any changes made to the protocol as deemed appropriate, but (in any case) at least once a year. The investigator must also keep the IRB informed of any AEs of interest, according to the IRB policy.

3.2 Ethical conduct of the study

This study will be conducted in accordance with all applicable local and federal regulations. Regulatory authorities will be notified and consulted as required prior to, during, and after the conduct of the study

This clinical trial will be conducted in compliance with the protocol, International Conference on Harmonisation (ICH), GCP guidelines, and other applicable regulatory requirements.

3.3 Informed consent

The investigator is responsible for obtaining written informed consent from each individual participating in this study after adequate explanation in layman's terms regarding the nature of the study, along with the aims, methods, objectives, and any

potential risks. The ICF must be appropriately signed and dated by the subject or the subject's legally authorized representative and the person obtaining the consent (if required by the IRB) prior to conducting/obtaining any study-related assessments, including the discontinuation of any medications prohibited for the study.

If the ICF is amended during the study, the investigator must follow all applicable regulatory requirements pertaining to approval of the amended ICF by the IRB and use of the amended form (including for ongoing subjects).

During the course of the study, the subject will be informed in a timely manner if information becomes available that may be relevant to the subject's willingness to continue participation in the study. In case of AEs, the subject should inform the investigator, who then will make a judgment whether continuing in the study serves the subject's best interests. The subject, however, is free to withdraw consent at any time and for any reason, whether expressed or not.

Each ICF will contain contact information with a phone number the subject should contact if they have medical concerns 24 hours a day.

The original and any amended signed and dated ICFs must be retained at the study site; and a copy of the signed and dated written informed consent must be given to the subject or subject's legally authorized representative(s).

4 INTRODUCTION

4.1 Study background

This clinical study is a post approval study (PAS) being conducted to satisfy a condition of the June 4, 2015, PMA-S (P050052/S049) approval of Radiesse injectable implant indicated for hand augmentation to correct volume loss in the dorsum of the hand. The purpose of the PAS is to provide a radiological evaluation of hands after implantation with Radiesse. X-rays of the hands were not taken in the pre-market study (Merz protocol #P110607) of 113 subjects.

4.2 Study rationale

Radiesse dermal filler is radiopaque and shows no overt radiographic safety concerns in a study of 58 patients after facial implantation, with Radiesse not always visible on plain X-rays². This PAS study will evaluate if there are concerns after Radiesse implantation in the dorsum of hands, specifically if implantation interferes with radiological assessment by obscuring the bones of the hand.

For a greater understanding of potential radiographic concerns, this study will assess the effect of Radiesse volume over time. Enrolled subjects will have baseline dorsal hand grades ranging from moderate (MHGS grade 2) to very severe volume loss (MHGS grade 4). The volume of Radiesse required to correct the baseline hand condition will be lower for moderate volume loss and higher for very severe volume loss. Baseline X-rays will be taken before, and 1-and 6-months after treatment on all subjects. If bones are not visible on the 6-month X-rays, another set of X-rays will be taken at 12-months. In the clinical practice of dermal filler implantation, patients seek repeat treatments to sustain the aesthetic benefits. In this study, there will be the opportunity for each subject to have up to 3 repeat treatments during participation in the 24-month study. To evaluate potential radiographic safety concerns of cumulative volumes of repeat treatments over time, X-rays of the hands will be taken at 24-months on all subjects who receive 4 treatments in this study: initial treatment plus 3 repeat treatments.

4.3 Risk-benefit assessment

Potential risks associated with the injection of Radiesse into the dorsum of the hand to restore volume loss are similar to injections performed with any other commercially available cosmetic dermal filler, such as bruising, swelling and redness. A potential risk of participation in this study would be the potential obscuring of hand bones in X-ray images that might be taken in the event of a hand injury. For complete safety and risk information, see the Instructions For Use (IFU, **Appendix A**).

² Carruthers A, et. al., “Radiographic and computed tomographic studies of calcium hydroxylapatite for treatment of HIV-associated facial lipoatrophy and correction of nasolabial folds,” Dermatol Surg 2008, 34:S78-S84.

Lidocaine is approved as a local and regional anesthetic and will be mixed in-office with Radiesse. Potential side effects associated with lidocaine are a risk of participating in this study and include lightheadedness, nervousness, apprehension, euphoria, confusion, dizziness, drowsiness, ringing noise in the ears, blurred or double vision, vomiting, sensations of heat, cold or numbness, twitching, tremors, convulsions, unconsciousness, respiratory depression and arrest, slow heartbeat, hypotension, and cardiovascular collapse, which may lead to cardiac arrest. However, these side effects are unlikely to occur at the low doses of lidocaine being used in this investigation. Lidocaine is beneficial in terms of pain reduction during and after the study procedure.

Potential risks associated with X-ray imaging of the hand are those that are associated with the use of X-ray imaging, that include development of cancer later in life and tissue effects such as skin reddening and hair loss. The levels of ionizing radiation and duration of exposure to be used in this study are low and are not expected to result in tissue effects.

[figure not shown]
A potential benefit of participating in this study is to have correction of volume loss and reduction of the prominence of veins and tendons in the dorsum of 1 or both hands. Additional potential benefits of improving the appearance of the hands could include enhanced emotional well-being with improved satisfaction with the appearance of the hands, or the perception of having a more youthful appearance.

5 STUDY OBJECTIVES AND ENDPOINTS

5.1 Objectives

The primary objective of the study is to provide a preliminary assessment of the radiographic appearance of Radiesse material that has been injected into the dorsum of the hands. The assessment will be with X-rays, as interpreted by a remote imaging core lab. Based on preliminary radiographic data of Radiesse implantation in the face³, it is expected that Radiesse injection(s) in the hands will not obscure the bones as seen on plain X-rays of the hand; however, this is not being evaluated with hypothesis testing.

Other objectives of the study include evaluating the effectiveness of Radiesse implantation for very severe volume loss in the dorsum of the hands, the rate of device/injection-related severe adverse events, the safety of multiple retreatments with Radiesse in the dorsum of the hands.

5.2 Endpoints

The primary safety endpoint of the study is the incidence of obscuration of the bones of the hand at 1, 6, 12 and 24 months.

The secondary endpoints of the study are:

- MHGS at 1- and 6-months after initial treatment
- MHGS at 1- and 6-months follow retreatment for those receiving retreatment
- GAIS at 1- and 6-months after initial treatment
- GAIS at 1- and 6-months follow retreatment for those receiving retreatment
- MHQ at baseline, study exit, and other collected time points
- The rate of device/injection-related severe AEs at 1- and 6-months

³ Carruthers et al, “Radiographic and computed tomographic studies of calcium hydroxylapatite for treatment of HIV-associated facial lipoatrophy and correction of nasolabial folds,” Dermatol Surg 2008, 34:S78-S84.

⁴ Shauver et al, “The Minimal Clinically Important Difference of the Michigan Hand Outcomes Questionnaire,” Journal of Hand Surgery, March 2009, 34A:509-514.

[figure not shown]

Figure 1. Merz Hand Grading Scale (MHGS).

[figure not shown]

Table 1. Global Aesthetic Improvement Scale (GAIS).

RATING	DESCRIPTION
Very Much Improved	Optimal cosmetic result for the implant in this patient
Much Improved	Marked improvement in appearance from initial condition, but not completely optimal for this patient
Improved	Obvious improvement in appearance from the initial condition
No Change	The appearance is essentially the same as the original condition
Worse	The appearance is worse than the original condition
Much Worse	Marked worsening in appearance from the initial condition
Very Much Worse	Obvious worsening in appearance from the initial condition

6 INVESTIGATIONAL PLAN

6.1 Overall study design

This is a prospective, open-label 2 year PAS evaluating radiographic appearance of Radiesse implantation in the dorsum of the hands in 20 subjects (40 hands). All subjects will be new subjects who did not participate in the pre-market Radiesse hand treatment study (Merz #P110607). Subjects will be consented at 1 investigational site in the United States.

Multiple assessments will be performed at study visits. Some of the main assessments include:

- X-rays – X-rays will be taken at a licensed radiographic imaging center and transmitted to the imaging core lab to be assessed by two blinded, licensed radiologists
- MHGS (**Figure 1**) – a single blinded site evaluator will grade the hands using the MHGS

- MHQ – subjects will self-report assessment of the effect(s) of Radiesse injection on hand function using the MHQ
- GAIS (**Table 1**) – subjects will rate the aesthetically pleasing aspect of the Radiesse hand treatment using the GAIS
- AE Subject Diary – subjects use this to collect any AEs for 30 days post injection
- Photographs – at baseline and exit from the study, and during the study to document a serious or medically concerning adverse event in the hands.

6.1.1 Study visits

Subjects will be required to present for a total of up to 15 visits and 4 follow up phone calls. Of these visits, 7 to 10 are in-office investigational site visits and an additional 3 to 5 are X-ray visits at a licensed radiology center, and 1 to 4 are follow-up phone calls during their 24-month study participation.

If a subject only receives the initial treatment at enrollment, there will be a total of 7 in-office clinic visits, 3 x-ray visits and 1 follow-up phone call. For each of the 3 optional repeat treatments received, there will be an additional follow-up phone call (72 hours post injection). The fourth x-ray visit will only be required at Month 12 if no bones are visible

at the 6 month x-ray and the fifth x-ray visit will only be conducted if a subject receives four total treatments of Radiesse in this PAS study.

Following consent and enrollment at the site, subjects will have X-rays taken of their hands at the radiology imaging center. Each digital radiographic image taken in the study will be assessed by 2 independent blinded, licensed radiologists at the radiology core lab. After X-rays, all subjects will return to the study clinic to receive Radiesse treatment.

At 1-month, all subjects will have X-rays of their hands taken and will be assessed by the treating investigator for AEs.

At 6-months after enrollment, all subjects will have X-rays of their hands taken prior to receiving a repeat Radiesse treatment, if Radiesse retreatment is agreed upon by treating investigator and subject.

Subjects will have X-rays of their hands at 12-months only if bones of the hands were reported to be obscured by Radiesse by at least 1 radiologist on the 6-month X-rays, and will be assessed by the treating investigator for AEs. Subjects will receive repeat Radiesse treatments at 12- and 18-month follow-up visits if Radiesse retreatment is agreed upon by treating investigator and subject. If X-rays of the hands are required at 12 months, they will be taken prior to Radiesse retreatment.

Subjects will have X-rays at 24-months only if they receive 4 Radiesse treatments in the study; at enrollment, 6-, 12-, and 18-months after enrollment.

An additional 1-month follow-up visit and 72-hour follow-up phone call will be scheduled after each repeat treatment received at the 6-, 12-, and 18-month visits which would be at 7-, 13-, and 19-months, respectively.

6.1.2 *End of study*

[figure not shown]
The end of study will be defined as completion of all study visits by all enrolled subjects during the 24-month participation period. If an unforeseen device-related serious adverse event (SAE) or unanticipated serious adverse device effect (USADE) occurs, the end of the study will be prolonged until clinical resolution of the event.

The study or parts of the study may be discontinued by Merz North America, Inc. (Merz) or at the recommendation of an investigator after consultation with Merz at any time. This may be based on a significant number of AEs of a similar nature that warrant such action or at the request of Merz.

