6.1.3 Study flow chart

Figure 2. Study design showing Radiesse treatment visits and X-ray schedule. Group A will be subjects with MHGS grade 4 hands at enrollment. Group B will be subjects with MHGS grade 2 or grade 3 hands at enrollment.

The figure does not show the initial screening visit or follow-up visits that will be scheduled 1-month after each optional retreatment received in the study.

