3. Locate the initial site for injection. Subjects are to receive injections in the dorsum of the hands between the 1st and 5th metacarpals. Injection should initially occur between the 2nd and 4th metacarpals, taking care not to inject close to the metacarpophalangeal joints. If necessary to achieve optimal correction, injection is also allowed between the 1st and 2nd, and 4th and 5th metacarpals.
4. Skin tenting should be performed to separate the skin from vascular and tendinous structures by using the thumb and forefinger of the non-injecting hand to lift skin over the dorsal aspect of the hand being treated.
5. Advance the needle between the subcutaneous layer and superficial fascia with the syringe parallel to the dorsum of the hand. Carefully push the plunger of the Radiesse injectable implant syringe to start the injection and inject the Radiesse injectable implant material in small boluses, 0.2 – 0.5cc/bolus. No more than 0.5cc should be injected per bolus. The number of boluses will vary depending on the extent of treatment desired. No more than 3cc of Radiesse injectable implant (2 syringes) will be injected per hand, per treatment session.
6. If significant resistance is encountered when pushing the plunger, the injection needle may be moved slightly to allow easier placement of the material or it may be necessary to change the injection needle.
7. Immediately after injection, cover the injection site with a sterile 4x4 gauze and have the subject sit on this hand while the contralateral hand is being injected.

This warms the Radiesse injectable implant making it more malleable for later massaging.

8. Treat the contralateral hand in the same manner as described in steps 2 through 6 above.
9. Immediately after injection of the contralateral hand, cover the injection site with a sterile 4x4 gauze and have the subject sit on this hand.
10. While the contralateral hand is warming, remove the gauze from the hand that was initially injected, have the subject make a fist with this hand, and gently massage the dorsum of the hand until Radiesse has been evenly spread across the dorsum, remaining distal to the wrist crease and proximal to the metacarpophalangeal joints.
11. Use a 1:1 correction factor. No overcorrection is needed.

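### Protocol 6.1.1 and SAP Section 2 each give two different exclusive triggers for the Month 12 X-ray, so whether a subject partly obscured at Month 6 is filmed again depends on which sentence is followed

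*Protocol*

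**What the plan says.** The readable protocol text states the Month 12 trigger five times.

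- 6.1.1, in the paragraph that counts visits: "The fourth x-ray visit will only be required at Month 12 if no bones are visible" at Month 6.
- 6.1.1, in the paragraph on the Month 12 visit: films are taken "only if bones of the hands were reported to be obscured by Radiesse by at least 1 radiologist on the 6-month X-rays".
- 4.2: "If bones are not visible on the 6-month X-rays, another set of X-rays will be taken at 12-months".
- 9.2, Month 12 X-rays: limited to subjects whose hand bones could not be seen at Month 6.
- Table 2, footnote: the same idea, applied if it holds for one hand or more.

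SAP Section 2 carries over three of these: the 4.2 sentence and both 6.1.1 sentences. Figure 2 is captioned "Study design showing Radiesse treatment visits and X-ray schedule". It is not legible in the copy available, so whether it states a trigger could not be checked.

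Month 12 is a named time point of the primary endpoint, the "incidence of obscuration of the bones of the hand at 1, 6, 12 and 24 months" (5.2), and 12.4.1 plans an exact 95% interval at each visit. Protocol 12.2 counts a film as obscured when either of the two core-lab radiologists reads it so, with no minimum extent, and 12.3.1 counts a subject on either hand. Protocol 9.1.4 makes the Month 6 reading decide who is scheduled at Month 12, but does not say which element of that reading decides. SAP Section 4 bases all analyses on observed data.

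**The concern.** Both 6.1.1 sentences are restrictive (each uses *only*), so they cannot be treated as two routes to the same film. One requires complete loss of visibility and the other requires obscuration of any extent reported by one reader. No readable text says which governs.

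The subjects caught between them matter most for the question at Month 12. They are primary events at Month 6, and the Month 12 film would show whether the obscuration persists. Without that film, the next scheduled one is at Month 24, and "Subjects will have X-rays at 24-months only if they receive 4 Radiesse treatments in the study". A subject who skips any retreatment would have no further scheduled imaging. Under the observed-data rule the subject would simply be absent from the Month 12 result.

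**Working it through.** **1. The plan's own count.** In-office visits: screening, Week 1 and Months 1, 6, 12, 18, 24 = 7, plus Months 7, 13, 19 = 10. X-ray visits: baseline, Months 1 and 6 = 3, plus conditional Months 12 and 24 = 5. Total 10 + 5 = 15, as 6.1.1 states. The count is the same under either trigger, so it does not help choose between them.

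**2. The five protocol statements side by side.**

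| Place | Condition at Month 6 | Reader rule | Hand rule |
|---|---|---|---|
| 6.1.1, visit count | no bones can be seen | none | none |
| 6.1.1, Month 12 visit | obscured by Radiesse, any extent | at least 1 of 2 | none |
| 4.2 | bones cannot be seen | none | none |
| 9.2 | bones cannot be seen | none | none |
| Table 2 footnote | bones cannot be seen | none | at least 1 hand |

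Reader rule: 1 of 5. Hand rule: 1 of 5. Both: 0 of 5.

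**3. What the two 6.1.1 sentences do with each kind of Month 6 reading.**

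| Month 6 reading | Visit-count sentence | Radiologist sentence |
|---|---|---|
| No obscuration | no film | no film |
| Some bones obscured by Radiesse, others visible | no film, read literally | film |
| One reader reports no bones visible, the other sees bones | indeterminate | film, if attributed to Radiesse |
| Both readers report no bones visible, attributed to Radiesse | film | film |

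**4. How many subjects are affected.** Let *a* be the number obscured at Month 6 according to at least one reader, and *b* the number with no bones visible. If loss of visibility is attributed to Radiesse, then *b* ≤ *a* ≤ 20, and *a* − *b* subjects are filmed under one sentence and not the other. The documents give neither value.

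**5. Illustration (assumed inputs, films actually taken as denominator, per SAP 4).** Take *a* = 4, with 2 of the 4 still obscured at Month 12.

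- Radiologist sentence: 4 film sets, result 2/4 = 50%. The exact lower limit solves P(X ≥ 2 | n = 4, p) = 0.025, giving 6.8%. The upper limit solves P(X ≤ 2 | n = 4, p) = 0.025, giving 93.2%.
- Visit-count sentence with *b* = 0: 4 − 0 = 4 subjects unfilmed and no Month 12 estimate.
- With *b* = 4: 4 − 4 = 0, and the two sentences give the same result.

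Range over other assumed inputs, taking none still obscured at Month 12 (upper exact 95% limit):

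| *a*, *b* | Radiologist sentence | Visit-count sentence |
|---|---|---|
| 4, 0 | 0/4: 60.2% | no data |
| 4, 1 | 0/4: 60.2% | 0/1: 97.5% |
| 10, 2 | 0/10: 30.8% | 0/2: 84.2% |

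**6. What does not move.** With the same attribution condition, everyone filmed at Month 12 under either sentence was already an event at Month 6, so any-time incidence is fixed. Months 1 and 6 are filmed in all subjects, and Month 24 depends only on the number of treatments.

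**The case against.** The strongest reply is that this is loose drafting and not two designs. The visit-count sentence sits in a logistics paragraph. The later sentence sets out the Month 12 visit, names who makes the call, and uses the same reader rule as 12.2. The injection procedure has filler massaged while "remaining distal to the wrist crease and proximal to the metacarpophalangeal joints", so losing sight of every bone is unlikely, and a literal rule would leave a named primary time point almost without films. On this view the visibility wordings are shorthand for obscured.

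That reading is plausible, but the documents do not state it. The visibility wording is also what 9.2 and Table 2 carry, and a site would schedule from those. Even as shorthand, it gives no rule for two readers who disagree.

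It also stands that the study is descriptive, tests no hypothesis, and that "it is expected that Radiesse injection(s) in the hands will not obscure the bones as seen on plain X-rays of the hand". If that expectation is met at Month 6, the conflict has no effect.

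Three stronger inferences are not supported:

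- A reader might infer that a subject flagged by one radiologist only is plainly excluded by the visit-count sentence. That sentence has no reader rule, so where one reader reports no bones visible the outcome is indeterminate. Only partial obscuration gives a clear conflict.
- A reader might take the two triggers as always nested. The visibility wordings name no cause, so nesting holds only when the loss is attributed to Radiesse.
- A reader might compare 2/20 with 0/20 at Month 12. That counts unfilmed subjects as not obscured, contrary to SAP 4.

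**Conclusion.** The text conflict is certain. The same two incompatible conditions stand in Protocol 6.1.1 and SAP Section 2, and no readable passage resolves them. It should be fixed because it decides which endpoint-positive subjects are filmed at a primary time point.

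Its reach is narrow. It affects only the composition of the Month 12 result, and only if at least one subject is obscured at Month 6 without all bones being hidden, or the readers disagree about visibility. In the illustration the Month 12 result is either 2/4 with an interval from 6.8% to 93.2%, or absent. An interval that wide means the issue is who is imaged, not a measurable difference in rate. The figures rest on assumed event counts and on loss of visibility being attributed to Radiesse. The finding does not call the primary endpoint as a whole into question.

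**What to change.** Reconcile Protocol 4.2, 6.1.1, 9.2, the Table 2 footnote and SAP Section 2 (and Figure 2 if it states a trigger) to one Month 12 imaging trigger. State the reader rule and the hand rule explicitly. Either make the trigger consistent with the obscuration definition in 12.2 and 12.3.1, or justify the difference. Have the Month 6 core-lab result used under 9.1.4 report that trigger directly. The choice of trigger is the sponsor's, and 12.1 records an interest in limiting radiation.

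The cost is wording changes in two documents and possibly one field on the core-lab report, which is not among the documents. The downside is at most one extra Month 12 film set per partly obscured subject, so at most 4 sets in the illustration. If the narrower trigger is chosen there are no extra films, but those subjects have no Month 12 result, and the SAP should say so.

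Separately, either trigger selects subjects on their Month 6 reading, and reconciliation will not remove that. SAP 6.1 should therefore report the Month 12 result as conditional on the Month 6 reading, with the number filmed as its denominator.
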